Page 31 5.2 Serious Adverse Events (SAEs) Original: Not previously included.	Page 31 5.2 Serious Adverse Events (SAEs) Addition: Definition: An adverse event that is any undesirable experience associated with the use of a medical product in a patient that results in death, hospitalization (new or prolonged), disability or permanent damage, or is life-threatening. Specific to this protocol, SAEs are defined as AEs with CTCAE v4.0 grade 3 or higher resulting in hospitalization or grade 4-5 AE. Treatment-related SAEs were SAEs that are possibly, probably, or definitely related to protocol treatment.
Page 32 5.8 Timeframe for Reporting Required Events Original: Not previously included.	Page 32 5.8 Timeframe for Reporting Required Events Clarification: Adverse events captured in the CRFs will be tracked for 12 months following SBRT. For the purposes of this protocol, reportable adverse events are grade 3, 4, or 5 toxicities that did not predate SBRT and are possibly, probably or definitely attributable to treatment. Patients will be assessed using the CTCAE v4.0.
Page 33 7.0 Study Calendar Original: Included up to 12 months of follow up.	Page 33 7.0 Study Calendar Administrative Change: The calendar was updated to match the previously approved Informed Consent Document. Extended follow up time point added to collect medical history, device interrogations, and adverse event assessment. The extended follow up time frame will last up to 5 years post-completion of study treatment.
Page 34 8.0 Data Submission Schedule Original: Follow-Form included up to 12 months post-SBRT for the submission schedule.	Page 34 8.0 Data Submission Schedule Addition: Addition of 2 years post-SBRT, 3 years post-SBRT, 4 years post-SBRT, and 5 years post-SBRT for the submission schedule for the follow-up form.

1.0 BACKGROUND AND RATIONALE

1.1 Ventricular tachycardia (VT) and sudden cardiac arrest (SCA)

Sudden cardiac arrest (SCA) is the single largest cause of death in the developed world. In the United States, over 325,000 deaths are due to SCA; more than lung cancer, breast cancer and AIDS combined [1]. A majority of SCA is due to cardiac arrhythmias, namely ventricular tachycardia (VT). Underlying cardiomyopathies and scarring most often cause ventricular arrhythmias. The scar from the cardiomyopathy (i.e., previous heart attack) forms the substrate for abnormal electrical circuits within the heart, which causes VT. Survival from an out-of-hospital SCA is only 10%. Patients who survive SCA have an estimated 40-60% chance of developing another ventricular arrhythmia in the subsequent year. [2, 3]

1.2 Current management of VT

For patients who have survived SCA from VT, the current clinical management strategy consists of two goals: 1) prevent the arrhythmia from happening again and 2) protect the patient from dying if the arrhythmia does happen again.

The second goal (protection) consists of installation of an implantable cardiac defibrillator (ICD) into the body. This device is used to deliver a burst of energy (shock) to restore regular rhythm if VT were to recur. While life-saving, shocks from an ICD are painful to patients and repeated shocks lead to a poor quality of life, largely driven by anxiety and depression [4-6]. Some evidence has also linked ICD shocks to increased risk of death [7].

To prevent VT and subsequent ICD therapies, patients can opt to take oral antiarrhythmic medications. Long-term medication use usually consists of administration of amiodarone, which has a significant cumulative adverse effect profile, including toxicities to hepatic, pulmonary, thyroid, skin, ophthalmologic and neurologic systems. An invasive catheter ablation procedure is often viewed as second-line, adjunctive therapy for the management of VT after failure of medication. This procedure generally takes 4-8 hours, often uses general anesthesia, and requires access to the inside of the heart through the veins or arteries of the leg or access to the outside of the heart through the skin underneath the breastbone. Long flexible catheters are inserted and maneuvered to identify critical components of the abnormal electrical circuit that causes VT. Once identified, radiofrequency energy is applied to the tip of the catheter (usually 3.5mm tip) to heat up the critical tissue to the point of cellular destruction (ablation), thus rendering it electrically inert. These critical components of the circuit are often located within abnormal cardiac tissue, most commonly from previous myocardial infarctions.

Despite important advances in invasive cardiac mapping and catheter ablation technologies, the success rates of catheter ablation to prevent VT in patients with

structural heart disease remain modest. Five randomized clinical trials of VT ablation procedures have been performed [8-12] and are summarized in a recent meta-analysis [13]. Other large multi-center studies have been published which did not randomize catheter ablation against medical therapy but are nonetheless important when assessing the overall success rates of this therapy [14-17]. In the meta-analysis that included 457 participants with largely ischemic cardiomyopathy and mean left ventricular ejection fraction of 30-35%, the recurrence rate of VT was 35% (range 12-50%) with catheter ablation (n=266) during a follow up of 6-22 months. This compared favorably to a recurrence rate of 55% (range 33-75%) in the medical-only control group (n=191). In other large prospective observational studies, risk of VT recurrence at one year after extensive catheter ablation approaches 50% [14-17].

VT ablation procedures can “fail” for many reasons. Commonly cited limitations include: 1) inability to map hemodynamically unstable VT; 2) difficult mapping due to multiple different VT circuits; 3) inability to create necessary radiofrequency ablation due to depth of myocardial scar; 4) inability to reach the critical component of the VT circuit with a catheter; 5) protective structures (i.e., epicardial fat) around the critical component of the VT circuit; and 6) late development of new abnormal circuits through myocardial scar after the original ablation. Methods to improve the success of VT ablation procedures need to address these key limitations. Examples of alternative methods in development for enhanced tissue destruction include: 1) injection of alcohol into smaller blood vessels to induce larger myocardial infarction; 2) development of catheters with extendable needles to impale ventricular myocardium to allow deeper radiofrequency ablation; and 3) using two ablation catheters to encircle the critical component of the scar in hopes of deeper penetration of thermal energy.

Because of its invasive nature, there are risks to a catheter ablation procedure. Risks of serious complications include death (3%), stroke/transient ischemic attack (1-2%), cardiac perforation (1-2%), third-degree heart block (1.6%), pericardial effusion/tamponade (1%), worsening heart failure and cardiogenic shock (1-2%), uncontrollable VT (1%), and sepsis (<1%). Anecdotally, several centers report higher rates of adverse events in patients with more advanced and global cardiomyopathies. Future improvements in VT ablation technologies will need to address these significant adverse event rates, particularly among the sickest patients, and for those who have already failed traditional catheter ablation. A noninvasive approach to cardiac ablation has the potential to significantly improve safety and provide a viable option for VT refractory to ablation and medication. An attractive alternative to thermal ablation with radiofrequency energy may be noninvasive stereotactic radiotherapy.

[figure not shown]
1.3 Stereotactic body radiotherapy (SBRT)

[figure not shown]
Stereotactic body radiotherapy (SBRT), also known as stereotactic ablative radiotherapy (SABR) or stereotactic radiosurgery (SRS), is a culmination of several decades worth of progress in radiation oncology, allowing for the precise delivery of high doses of radiation

to targets in the body over few (typically, < 5) fractions with minimal exposure of normal adjacent tissue. [18]

Such treatments have been successfully used to treat malignant and benign tumors in all body sites, most commonly in the brain, lung, liver, and spine. Advances in image guidance (orthogonal kV:kV imaging, conebeam CT (CBCT), etc.) and motion management (4D-CT, internal and external fiducials, etc.) have been central to the success of SBRT, particularly for tumors that are mobile. For example, it is now well established by multiple prospective clinical trials that SBRT delivered over 3-5 fractions results in local control rates > 90% for inoperable early stage lung cancer, with remarkably low rates of toxicity (<5-10% risk of grade 2+ pneumonitis, 15% risk of grade 1+ chest wall pain).[19, 20]) An example of a typical lung cancer SBRT plan and follow-up is provided in Figure 1.

Figure 1. (A) SBRT treatment plan. (B) Pre-treatment, planning volume, and post-treatment images.

All manufacturers of modern radiotherapy delivery systems have SBRT options or capabilities, with a variety of different methods for delivery. None of these delivery methods has been shown to be any more successful at delivering SBRT treatments than another when performed in the context of a carefully commissioned machine and workflow including standardization of immobilization, imaging, planning techniques and tissue constraints, and plan and machine QA. To this end, SBRT has now become a commonly used and mainstream method for tumor treatments with rapidly expanding indications.

1.4 SBRT for arrhythmia

Preclinical dose finding studies in porcine models have demonstrated that large (25 to 35 Gy), single fraction doses of SBRT can be accurately delivered to discrete targets in the heart, resulting in fibrosis that correlates to electrical isolation, similar to that found in catheter ablation. [21-26] In the earliest of these publications, Maguire *et al* reported on single fraction Cyber Knife radiosurgery (25 Gy (N=1), 35 Gy (N=1)) delivery to the right superior and left superior pulmonary veins in two Hanford mini-swine. [21] Animals were followed for six months and underwent electrophysiology (EP) testing, transesophageal echocardiography, and subsequently pathologic analysis. At the last time point, the EP study documented intended pulmonary vein isolation (electrical block) using a decapolar Lasso catheter, and echocardiographic monitoring of atrial and ventricular function six months post radiosurgery demonstrated normal cardiac function. Histologic analysis showed transmural fibrosis and contiguity of the ablation scar within the target. No adverse events were noted.

In a follow-up study from the same group, Sharma *et al* reported results from a dose (25 to 50 Gy) and location response experiment using single fraction Cyber Knife radiosurgery in 16 Hanford-Sinclair mini swine. [23] Targets included the cavotricuspid isthmus, AV node, pulmonary vein–left atrial junction, or left atrial appendage. Ranging from 25 to 196 days after treatment, animals were investigated with repeat electroanatomic voltage mapping and transesophageal echocardiography, when possible. The animals then were sacrificed and pathology specimens taken. Dose finding suggested that 25 Gy was the

minimum dose needed to produce an electrophysiologic effect, and this was consistently observed by 90 days. The method was deemed feasible for producing bidirectional cavotricuspid isthmus block and AV nodal conduction block. In addition, the pulmonary vein–left atrial junction and left atrial appendage showed marked voltage reduction to less than 0.05 mV. Histologic analysis demonstrated effects consistent with radiotherapy effect confined to the targeted areas with no evidence of damage outside the heart.

In a more recent publication from Blanck *et al*, a dose response experiment was performed on 9 mini-pigs (0 Gy and 17.5-35 Gy in 2.5-Gy steps) delivered to the right superior pulmonary vein. [7] Baseline MRI and electrophysiology were performed at baseline and 6 months after treatment. In contrast to the CyberHeart group, transmural scarring of cardiac muscle tissue was noted with doses ≥ 32.5 Gy. Likewise, complete circumferential scarring of the RSPV was not achieved at any dose level. Heart function was not affected, as verified by MRI and electrocardiogram evaluation. Adjacent critical structures were not damaged, as verified by pathology.

While the reasons for discrepancy in the required single fraction dose for effect are somewhat unclear, part of the difference may stem purely from subtleties in differences in dose planning and delivery for a given prescription dose. In the studies from the CyberHeart group, for a prescription dose of 25 Gy, maximum doses in the target volume may have exceeded 120-130% of prescription dose (Max doses > 30 -39 Gy). In contrast, in the study from Blanck *et al*, for a suggested dose of 32.5 Gy, the maximum dose to the target with their delivery system would generally not exceed 107% of prescription dose by convention (Max dose 35 Gy). As such, both studies may in fact be suggesting the same dose range for effect, despite the differences in prescription dose.

delivering single fraction SBRT to discrete areas in the heart for purposes of creating scar and reducing arrhythmia burden. Similarly, though the literature base is quite small and median follow-up short, there are now at least 5 documented cases in the literature of successfully delivering SBRT to 25 Gy in a single fraction for refractory arrhythmia (4 VT, 1 atrial fibrillation). Thus, the early safety and promising efficacy results, particularly in the at risk VT population who often have limited options (continued medical management, heart transplant, or hospice, etc.), justifies exploring this noninvasive strategy further.

1.5 Electrocardiographic Imaging (ECGI): Noninvasive Electrical Mapping

The scattered previous reports of noninvasive cardiac ablation have been performed in the absence of detailed electrical mapping. Washington University has been at the forefront of developing a noninvasive cardiac mapping system, called Electrocardiographic Imaging (ECGI), which is an important development toward improving four-dimensional precision of imaging cardiac electrophysiology. This is a noninvasive imaging approach, similar to CT or MRI, except that it is designed to image cardiac electrical function. In brief, ECGI measures body surface electrical potentials at over 200 sites on the torso. It incorporates the patient-specific anatomy of the heart with the recording leads on the body surface to noninvasively reconstruct the electrical activity on a three-dimensional model of the patient's heart surface.

This modality has been validated extensively in animal and tank-torso models. It has been used to image cardiac electrophysiology in a number of normal and disease states in humans as well. [32-41]

ECGI represents an important link in the development of an entirely noninvasive mapping & ablation system, as it adds noninvasive electrophysiologic mapping to the other noninvasive myocardial scar imaging (from standard modalities such as echo, SPECT, MRI) to provide the most accurate plan for noninvasive ablation.

In all of the clinical cases reported in the literature to date, treatment was delivered using the CyberKnife, a robot linac with orthogonal kV:kV image guidance. Such a delivery system allows for diverse treatment to all sites of the body, but does require placement of a fiducial for x-ray image guidance, and due to the nature of the step-and-shoot delivery of the robot linac, treatment times average 1.5 hours.

At Washington University, all treatments delivered to date have been on an image-guided radiotherapy (IGRT)-equipped linear accelerator per our typical lung SBRT workflow. These units are equipped with an onboard cone beam CT (CBCT) which allows for acquisition of high fidelity volumetric images of the thorax which can be directly registered to the planning CT, allowing for accurate, near real time alignment of the heart and target volume. This precludes the need for invasive placement of a fiducial marker. In comparison, VMAT treatment times for our patients have averaged approximately 10

minutes. Figure 3 is an example of a ENCORE treatment plan for patient #1. In all cases, overall treatment time is substantially faster than the previously reported cases in the literature, which results in improved patient comfort and may also improve overall delivery accuracy, as increased time on the treatment machine has been correlated with “drift” away from the isocenter over time. [31]

Unlike other centers, treatments at Washington University have been delivered to regions that combine anatomic and electrical abnormalities. Anatomic abnormalities are defined as regions of ventricular scar, determined from clinical cardiac imaging modalities such as delayed-enhancing cardiac MRI (DE cMRI), nuclear computed tomography (SPECT) and/or previous intracardiac mapping. Electrical abnormalities are identified by 12-lead ECG during a clinical VT or 12-lead ECG during an induced VT from a noninvasive programmed stimulation procedure (NIPS). Figure 3 is an example of a ENCORE treatment plan developed for patient #1, targeting an area of anatomic scar that was identified with DE cMRI which overlapped with the area of electrical abnormalities based on 12-lead ECGs of VT obtained during NIPS. The results for each patient are depicted in the bar graph.

Figure 3. ENCORE procedure. TOP LEFT—Cardiac MRI demonstrating the extensive mid-myocardial scar (yellow arrows); TOP MIDDLE—Noninvasive electrical mapping (ECGI) performed during VT; TOP RIGHT—Noninvasive ablation treatment plan (light green is target volume) combining electrical and anatomic information; BOTTOM—Stereotactic radiotherapy delivered with 2 VMAT noncoplanar arcs to 25 Gy/single fraction.

As such, the delivery methods within this protocol are novel inasmuch as they are 1) rapid; 2) entirely non-invasive; 3) guided by noninvasive imaging of the electrical and structural abnormalities.

1.7 Study Rationale

Patients with VT either refractory to catheter ablation or deemed medically too frail or challenging to treat with catheter ablation have limited options, with one-year survival below 20%. Preclinical data described above demonstrate that single fraction SBRT to discrete portions of the heart is feasible and may result in a reduction or elimination of VT. Overall safety and early efficacy of SBRT have not been rigorously studied in a prospective trial to date. The ENCORE therapy described herein provides for a potentially rapid and totally non-invasive method for delivering such therapy.

The purpose of this phase I/II study is to demonstrate the short-term safety and preliminary efficacy of ENCORE for patients with VT refractory to standard treatments.

2.0 OBJECTIVES

2.1 Primary Objectives

1. Phase I - Demonstrate acute (≤ 90 days) safety of noninvasive stereotactic cardiac ablation radiotherapy (ENCORE). The **primary safety endpoint** is defined by a $\leq 20\%$ rate of serious adverse events (SAEs) using CTCAE v4.0 criteria that are possibly/probably/definitely related to study treatment, based on previously published data for expected invasive catheter-based VT-ablation procedures.
2. Phase II - Demonstrate preliminary efficacy of ENCORE. The **primary efficacy endpoint** is defined by the number of subjects with a reduction in ICD therapies (ATP and ICD shocks) comparing the period six months before ENCORE treatment to the six months after ENCORE treatment as adjudicated by continuous ICD monitoring. There will be a six-week “blanking period” after therapy to allow for ablation effect. For patients with PVC-induced cardiomyopathy, the primary efficacy will be any reduction in PVC burden based on ambulatory heart monitors.

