3.0 PATIENT SELECTION

3.1 Inclusion Criteria

1. DOCUMENTED VT:
 - a. Patient must have documented sustained monomorphic ventricular tachycardia as documented on either a 12-lead ECG or intracardiac ICD interrogation
 - OR—
 - b. Monomorphic PVCs documented on a 12-lead ECG.
2. ANTIARRHYTHMIC MEDICATION: Patient must have failed or become intolerant to at least one antiarrhythmic medication (amiodarone, sotalol, or mexiletine).
—AND—
3. CATHETER ABLATION: Patient must have failed at least one invasive catheter ablation procedure, or have a contraindication to a catheter ablation procedure (e.g., LV thrombus, severe pulmonary disease), or have VT thought to arise from a protected location (e.g., epicardial VT with history of previous cardiac surgery).
4. MINIMUM VT BURDEN: Patient must have either:
 - a. At least 3 VT episodes (sustained VT, ICD ATP or ICD shock) over previous 6 months prior to enrollment
 - OR—
 - b. >20% PVC burden with a cardiomyopathy (LVEF<50%)
5. Patient must be deemed medically fit for stereotactic body radiation therapy by the treating physician.
6. Patient must be \geq 18 years old.
7. Patient must be able to understand and be willing to sign an IRB approved written informed consent document.

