7.0 STUDY CALENDAR

	Screening	Baseline	ENCORE tx	Day 3	2 wk	4 wk	6 wk	3 mo	6 mo	12 mo	Extended F/U**
Informed consent	X										
Medical history	X										X
Pregnancy test	X										
Device interrogation (Standard of care)	X		X	X	X	X	X	X	X	X	X
24 Hour heart monitor* (Standard of care)	X						X	X	X	X	
SF-36 QoL		X					X		X	X	
12-lead EKG		X		X			X	X	X	X	
NIPS		X									
Cardiac CT + ECGI		X						X		X	
Cardiac MRI + PET		X		X				X			
Adverse events assessment		X	X	X	X	X	X	X	X	X	X
Blood work		X		X			X	X			

* For patients with PVC-induced cardiomyopathy-indications only

** Patients will be followed as per routine clinical practice, with data being collected from the medical record on outcomes for up to 5 years post-completion of study treatment. Device interrogation, 24 hour heart monitors, and imaging will be performed as clinically indicated but are not mandated by the protocol. Capture of AEs will be performed as described in Section 5.1.

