11.2 Sample Size Justification

A total of 19 patients will be enrolled, which provides an optimal balance between assuring a high likelihood of safety (Phase I) with a preliminary assessment of efficacy (Phase II).

For the phase I component, the baseline rate of SAEs for catheter ablation is assumed to be 10-15%. Given the population being studied and a reasonable expectation that patients may be at a higher than typical risk of toxicity from any salvage therapy, we assume that SAE rates up to 20% would be clinically acceptable. Having said that, given that this is a totally noninvasive technique, it may well be that rates of toxicity are lower than that expected with catheter ablation. After exploring patient ranges from 15-25 patients, it was determined that 19 patients would provide a 75.4% power to detect an SAE rate about 20% (range, 5%-20%, $\alpha = 0.0829$).

For the phase II component, while some single institution series report much higher success rates, the baseline efficacy rate of catheter ablation in prospective trials ranges from 50-65%. As this is a salvage therapy in a high risk population, we assume that efficacy rates as low as 40% would be clinically acceptable. Using the 19 patient sample determined above, it was determined that 19 patients would provide 81.5% power to determine that ENCORE is not worse than 40% effective for the treatment of VT (range, 40-65%, $\alpha = 0.0885$).

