11.3 Analytic Plan for Primary Objectives

SAEs defined by CTCAE v4.0 criteria within 90 days of ENCORE that are possibly/probably/definitely related to study treatment will be recorded. ENCORE therapy will be deemed safe if the rate of SAEs is $\leq 20\%$. An additional early stopping rule dictates that if 5 or more out of the first 10 patients develop ENCORE related SAEs, the trial will be halted.

The number of ICD therapies delivered in the 6 month periods preceding and following ENCORE therapy will be recorded for each patient by interrogation of the ICD. ENCORE therapy will be deemed efficacious if there is a reduction in ICD therapies before and after treatment. The proportion of patients with efficacious ENCORE therapy will be calculated, with the intent of demonstrating at least 40% efficacy.

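### For PVC-cardiomyopathy patients, the any-reduction success rule is met by chance at least about half the time, which is already above the 40% efficacy bar

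*Combined protocol and SAP*

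**What the plan says.** Section 2.1 (item 2) defines the main efficacy endpoint by ICD therapies, then adds a separate rule for PVC-induced cardiomyopathy: "the primary efficacy will be any reduction in PVC burden based on ambulatory heart monitors". It gives no minimum fall, follow-up visit, averaging rule or baseline recording.

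Entry criterion 4b in section 3.1 requires a PVC burden above 20% with LVEF below 50%. The Study Calendar (section 7.0) has a 24-hour monitor at screening, 6 weeks, 3, 6 and 12 months, footnoted "For patients with PVC-induced cardiomyopathy-indications only". Screening is the only pre-treatment time point for it.

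Section 11.2 sets the size and the bar: "A total of 19 patients will be enrolled", and "we assume that efficacy rates as low as 40% would be clinically acceptable". It quotes 81.5% power and alpha 0.0885 for 40% against 65%. Section 11.3 calculates the proportion of successes "with the intent of demonstrating at least 40% efficacy", but it describes success by ICD therapies only, as does section 9.0 (item 2). Neither mentions PVC patients.

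Section 2.2 already has a stricter PVC threshold, a reduction of more than 50% (item 4), as a secondary endpoint.

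**The concern.** A success rule can show efficacy only if it is met less often without a treatment effect than the bar requires. Any reduction in a quantity that varies from day to day is met by about half of patients whose burden has not changed. The bar is 40%, so among PVC patients an inert treatment would be expected to pass.

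Selection may make this worse. If the reading that got the patient in (above 20%) is also the baseline, some of those readings were high by chance, and the next reading tends to be lower.

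If PVC patients are pooled into the primary proportion, each one raises the no-effect success rate above 40%, and the test's real false-positive rate exceeds the quoted alpha.

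**Working it through.** **1. The plan's own figure.** With X ~ Binomial(19, p) and success declared at X ≥ r:
- r = 10: alpha (p = 0.40) 0.186, power (p = 0.65) 0.913
- r = 11: alpha 0.0885, power 0.8145
- r = 12: alpha 0.035, power 0.666

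The quoted 0.0885 and 81.5% reproduce at r = 11. The plan does not print this cut-off; it is inferred from the match.

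**2. Chance rate without selection.** Let B be the baseline and F the follow-up reading. With no effect and no drift the two are exchangeable, and ties are negligible, so P(F < B) = 1/2. No variance figure is needed, and 1/2 exceeds 0.40.

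**3. Chance rate if the baseline is selected as B > c, with c = 20%.** When both readings exceed c, each is the lower half the time. When B > c and F ≤ c, a fall is certain. Hence

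P(F < B | B > c) = 1/2 + 1/2 × P(F ≤ c | B > c).

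This cannot be below 1/2. How far above depends on day-to-day variability and the burden distribution, which the documents do not give. Assume normal true burden and error on the logit scale, with between-patient SD 0.7 and median burden 20%. Then the correlation is ρ = 0.7² / (0.7² + s²) and P(F ≤ c | B > c) = 1/2 − arcsin(ρ)/π:
- day-to-day SD s = 0.1: ρ = 0.98, 0.064, chance rate 0.53
- s = 0.3: ρ = 0.845, 0.180, chance rate 0.59
- s = 0.7: ρ = 0.50, 0.333, chance rate 0.67

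Simulation over assumed medians of 15–30%, between-patient SD 0.4–1.0 and day-to-day SD 0.1–0.7 gives 51–78% with one follow-up monitor. A log-normal version (medians 15–30%, between-patient SD 0.4–0.6, day-to-day SD 0.2–0.6, readings capped at 100%) gives 53–76%. If a fall on any one of the 6-week, 3-month or 6-month monitors counted, which the wording does not exclude, the logit model gives 76–97%.

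**4. Effect on the 40% test, if PVC patients enter it.** Let m PVC patients succeed with chance rate q and the other 19 − m with probability 0.40. The false-positive rate is P(Bin(m, q) + Bin(19 − m, 0.40) ≥ 11):

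| m | q = 0.50 | q = 0.60 |
|---|---|---|
| 0 | 0.0885 | 0.0885 |
| 1 | 0.096 | 0.104 |
| 3 | 0.113 | 0.141 |
| 5 | 0.132 | 0.186 |
| 10 | 0.189 | 0.337 |

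**5. The alternative rule.** Under the log-normal model with no effect, success means that the mean of two follow-up readings is below half the baseline. Keeping the eligibility reading as baseline, the chance rate is 0.2–0.6% at day-to-day SD 0.2, 8–17% at 0.4 and 18–34% at 0.6. It stays below 40% throughout. The same threshold on a single follow-up monitor reaches 41% at SD 0.6, so the averaging matters. With a pre-treatment reading separate from the eligibility one, the averaged rule gives about 0.2%, 6–7% and 12–15%.

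**The case against.** Three stronger readings are tempting, and the documents do not support them.

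- **That chance success is well over half.** Every figure above 50% rests on assumed variability. With stable burden, or most patients far above 20%, the rate stays near 51%. Upward drift in untreated burden, for example after drug reductions during follow-up (section 4.10), would lower it.
- **That the protocol uses the eligibility monitor as baseline and compares two single monitors.** This is an inference from the calendar. Criterion 4b does not say which recording must show more than 20%. The monitor is labelled standard of care, so an earlier clinical recording might qualify a patient. The endpoint refers to monitors in the plural and names no visit.
- **That the trial's false-positive rate is inflated.** Sections 9.0 and 11.3 define success by ICD therapies alone, so PVC patients may not enter the 40% test at all. The protocol describes a VT population in which most or all are expected to have ICDs. With few PVC patients the shift is modest.

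It can also be said that the aim is only preliminary efficacy, that stricter PVC thresholds are already secondary endpoints, and that choosing 50% over another margin is partly judgement. All of this stands as a limit on size. None of it removes the basic point: without drift, the no-effect rate of the stated rule is at least one half, above the bar, whatever the variability.

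**Conclusion.** The point holds in this form. For PVC patients the primary rule has a no-effect success rate of at least about 50%, assuming no drift, so meeting 40% on it says nothing about efficacy in them. The 51–78% range additionally assumes that the screening reading serves as baseline, one follow-up monitor, and the variability listed above.

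The trial-level effect is conditional. If PVC patients are counted, and succeed by chance at 50–60% while the rest succeed at 40%, alpha is about 0.096–0.104 with one, 0.113–0.141 with three and 0.132–0.186 with five. If they are not counted, the quoted alpha is unaffected, but section 2.1 then gives them a primary endpoint that the analysis plan never uses. This should be changed: it is a validity flaw in a primary endpoint definition, of modest size unless PVC patients are numerous.

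**What to change.** - In 2.1, define PVC success as a reduction of more than 50% (the threshold in 2.2 item 4), comparing the average of the scheduled 3- and 6-month monitors with a named pre-treatment recording. Where possible, use one other than the recording that established eligibility. Say what is used if one of the two follow-up monitors is missing.
- Report the proportion with any reduction descriptively.
- In 11.3, and to match in 9.0, state whether and how PVC patients enter the 40% test. Report the proportion for the VT/ICD patients separately.

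Cost: changes of wording and no extra follow-up monitors. A separate baseline can be an existing clinical recording where there is one. The downsides are a lower observed success proportion among PVC patients, a stricter threshold for them than for VT patients within one proportion, and overlap with the PVC part of secondary item 4, which would need rewording or dropping. The separate VT/ICD proportion keeps the mixed standard visible.
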